13.8. Termination of the Study

Celgene reserves the right to terminate this study prematurely at any time for reasonable medical or administrative reasons. Any premature discontinuation will be appropriately documented according to local requirements (eg, IRB/EC, regulatory authorities, etc.).

In addition, the Investigator or Celgene has the right to discontinue a single site at any time during the study for medical or administrative reasons such as:

- Unsatisfactory enrollment;
- GCP noncompliance;
- Inaccurate or incomplete data collection;
- Falsification of records;
- Failure to adhere to the study protocol.

14. DATA HANDLING AND RECORDKEEPING

14.1. Data/Documents

The Investigator must ensure that the records and documents pertaining to the conduct of the study and the distribution of the investigational product are complete, accurate, filed and retained. Examples of source documents include: hospital records; clinic and office charts; laboratory notes; memoranda; subject's diaries or evaluation checklists; dispensing records; recorded data from automated instruments; copies or transcriptions certified after verification as being accurate copies; microfiche; x-ray film and reports; and records kept at the pharmacy, and the laboratories, as well as copies of CRFs or CD-ROM.

14.2. Data Management

Data will be collected and entered into the clinical database via electronic CRF per Celgene SOPs. This data will be electronically verified through use of programmed edit checks specified by the clinical team. Discrepancies in the data will be brought to the attention of the clinical team, and investigational site personnel, if necessary. Resolutions to these issues will be reflected in the database. An audit trail within the system will track all changes made to the data.

14.3. Record Retention

Essential documents must be retained by the Investigator according to the period of time outlined in the clinical trial agreement. The Investigator must retain these documents for the time period described above or according to local laws or requirements, whichever is longer. Essential documents include, but are not limited to, the following:

- Signed ICFs for all subjects;
- Subject identification code list, screening log (if applicable), and enrollment log;
- Record of all communications between the Investigator and the IRB/EC;
- Composition of the IRB/EC;
- Record of all communications between the Investigator, Celgene, and their authorized representative(s);
- List of Sub-investigators and other appropriately qualified persons to whom the Investigator has delegated significant study-related duties, together with their roles in the study, curriculum vitae, and their signatures;
- Copies of CRFs (if paper) and of documentation of corrections for all subjects;
- IP accountability records;
- Record of any body fluids or tissue samples retained;
- All other source documents (subject records, hospital records, laboratory records, etc.);
- All other documents as listed in Section 8 of the ICH consolidated guideline on GCP (Essential Documents for the Conduct of a Clinical Trial).

The Investigator must notify Celgene if he/she wishes to assign the essential documents to someone else, remove them to another location or is unable to retain them for a specified period. The Investigator must obtain approval in writing from Celgene prior to destruction of any records. If the Investigator is unable to meet this obligation, the Investigator must ask Celgene for permission to make alternative arrangements. Details of these arrangements should be documented.

All study documents should be made available if required by relevant health authorities. Investigator or institution should take measures to prevent accidental or premature destruction of these documents.

15. QUALITY CONTROL AND QUALITY ASSURANCE

All aspects of the study will be carefully monitored by Celgene or its authorized representative for compliance with applicable government regulations with respect to current GCP and SOPs.

15.1. Study Monitoring and Source Data Verification

Celgene ensures that appropriate monitoring procedures are performed before, during and after the study. All aspects of the study are reviewed with the Investigator and the staff at a study initiation visit and/or at an Investigators' Meeting. Prior to enrolling subjects into the study, a Celgene representative will review the protocol, CRFs, procedures for obtaining informed consent, record keeping, and reporting of AEs/SAEs with the Investigator. Monitoring will include on-site visits with the Investigator and his/her staff as well as any appropriate communications by mail, email, fax, or telephone. During monitoring visits, the facilities, investigational product storage area, CRFs, subject's source documents, and all other study documentation will be inspected/reviewed by the Celgene representative in accordance with the Study Monitoring Plan.

Accuracy will be checked by performing source data verification that is a direct comparison of the entries made onto the CRFs against the appropriate source documentation. Any resulting discrepancies will be reviewed with the Investigator and/or his/her staff. Any necessary corrections will be made directly to the CRFs or via queries by the Investigator and/or his/her staff. Monitoring procedures require that informed consents, adherence to inclusion/exclusion criteria and documentation of SAEs and their proper recording be verified. Additional monitoring activities may be outlined in a study-specific monitoring plan.

15.2. Audits and Inspections

In addition to the routine monitoring procedures, a Good Clinical Practice Quality Assurance unit exists within Celgene. Representatives of this unit will conduct audits of clinical research activities in accordance with Celgene SOPs to evaluate compliance with Good Clinical Practice guidelines and regulations.

The Investigator is required to permit direct access to the facilities where the study took place, source documents, CRFs and applicable supporting records of study subject participation for audits and inspections by IRB/ECs, regulatory authorities (eg, FDA, European Medicines Agency [EMA], Health Canada) and company authorized representatives. The Investigator should make every effort to be available for the audits and/or inspections. If the Investigator is contacted by any regulatory authority regarding an inspection, he/she should contact Celgene immediately.

15.3. Product Quality Complaint

A Product Quality Complaint (PQC) is any written, electronic, or oral communication that alleges deficiencies related to the identity, quality, durability, reliability, safety, effectiveness, purity, or performance of any drug product manufactured by or on behalf of Celgene Corporation after it is released for distribution. Product Quality Complaints may reduce the usability of the product for its intended function or affect performance of the product and therefore pose a significant risk to the subject. Examples of PQCs include (but are not limited to): mixed product,

mislabeling, lack of effect, seal/packaging breach, product missing/short/overage, contamination, suspected falsified, tampered, diverted or stolen material, and general product/packaging damage. If you become aware of a suspected PQC, you are obligated to report the issue immediately. You can do so by emailing [REDACTED] or by contacting the Celgene Customer Care Center [REDACTED].

16. PUBLICATIONS

As described in Section 13.2, all protocol- and amendment-related information, with the exception of the information provided by Celgene on public registry websites, is considered Celgene confidential information and is not to be used in any publications. Celgene protocol-related information proposed for use in a publication must be submitted to Celgene for review and approval and should not be utilized in a publication without express written approval from Celgene, or as described in the Clinical Trial Agreement.

Celgene will ensure Celgene-sponsored studies are considered for publication in the scientific literature in a peer-reviewed journal, irrespective of the results. At a minimum, this applies to results from all Phase 3 clinical studies, and any other study results of significant medical importance. This also includes results relating to investigational medicines whose development programs have been discontinued.

Study results may also be presented at one or more medical congresses and may be used for scientific exchange and teaching purposes. Additionally, this study and its results may be submitted for inclusion in all appropriate health authority study registries, as well as publication on health authority study registry websites, as required by local health authority regulations.

Eligibility for external authorship, as well as selection of first authorship, will be based on several considerations, including, but not limited to, contribution to protocol development, study recruitment, data quality, participation in data analysis, participation in study steering committee (when applicable) and contribution to abstract, presentation and/or publication development.

18. APPENDICES

APPENDIX A. TABLE OF ABBREVIATIONS

Abbreviation or Specialist Term	Explanation
ADL	Activities of daily life
AE	Adverse event
ALP	Alkaline phosphatase
ALT	Alanine aminotransferase (SGPT)
ANCOVA	Analysis of covariance
ASK1	Apoptosis signal-regulating kinase 1
[REDACTED]	[REDACTED]
AST	Aspartate aminotransferase (SGOT)
ATP	Adenosine triphosphate
AUC	Area under the curve
[REDACTED]	[REDACTED]
[REDACTED]	[REDACTED]
[REDACTED]	[REDACTED]
AUDIT	Alcohol Use Disorders Identification Test
[REDACTED]	[REDACTED]
β-hCG	Beta-subunit of human chorionic gonadotropin
BID	Twice daily
BUN	Blood urea nitrogen
CBC	Complete blood count
[REDACTED]	[REDACTED]
[REDACTED]	[REDACTED]
CI	Confidence interval
CIOMS	Council for International Organizations for Medical Sciences, Working Group
[REDACTED]	[REDACTED]
[REDACTED]	[REDACTED]
[REDACTED]	[REDACTED]
C _{max}	Maximum plasma concentration of drug
CMH	Cochran–Mantel–Haenszel

APPENDIX A: TABLE OF ABBREVIATIONS (CONTINUED)

Abbreviation or Specialist Term	Explanation
CP	Child-Pugh
CRN	Clinical Research Network
CRF	Case report form
CS	Clinically significant
CTCAE	Common Terminology Criteria for Adverse Events
CVID	Common variable immunodeficiency
█	█
█	█
DM	Diabetes mellitus
DMC	Data monitoring committee
EC	Ethics Committee
ECG	Electrocardiogram
eCRF	Electronic case report form
eGFR	Estimated glomerular filtration rate
█	█
EtG	Ethyl glucuronide
EOT	End of treatment
ET	Early Termination
FAS	Full Analysis Set
FCBP	Females of childbearing potential
FDA	Food and Drug Administration
FIB-4	Fibrosis-4
FOBT	Fecal occult blood test
FSH	Follicle-stimulating hormone
GCP	Good Clinical Practice
GD	Gestation Day
GGT	Gamma-glutamyl transferase
GI	Gastrointestinal
GLP	Good Laboratory Practice
█	█

APPENDIX A: TABLE OF ABBREVIATIONS (CONTINUED)

Abbreviation or Specialist Term	Explanation
HbA1c	Hemoglobin A1c
HBsAg	Hepatitis B surface antigen
HBV	Hepatitis B virus
HCC	Hepatocellular cancer
HCV	Hepatitis C virus
HDL	High-density lipoprotein
HIV	Human immunodeficiency virus
██████████	██
IB	Investigator’s Brochure
ICF	Informed consent form
ICH	International Council for Harmonisation
IL	Interleukin
INR	International normalized ratio
IP	Investigational product
IRB	Institutional Review Board
ITT	Intent-to-treat
IWRS	Interactive web response system
IV	Intravenous
JNK	c-Jun N-terminal kinase
LDH	Lactic dehydrogenase
LDL	Low-density lipoprotein
██████	████████████████████
██████	████████████████████
LS	Least-squares
██████	██
██████	████████████████████
MCP-Mod	Multiple comparison and dose-response modeling
MED	Minimum effective dose
MedDRA	Medical Dictionary for Regulatory Activities
MMRM	Mixed model of repeated measures

APPENDIX A: TABLE OF ABBREVIATIONS (CONTINUED)

Abbreviation or Specialist Term	Explanation
[REDACTED]	[REDACTED]
[REDACTED]	[REDACTED]
NASH	Non-alcoholic Steatohepatitis
NAFLD	Non-alcoholic fatty liver disease
NAS	NAFLD Activity Score
NCS	Not clinically significant
NOAEL	No observed adverse effect level
NRI	Non-responder imputation
[REDACTED]	[REDACTED]
[REDACTED]	[REDACTED]
[REDACTED]	[REDACTED]
[REDACTED]	[REDACTED]
[REDACTED]	[REDACTED]
[REDACTED]	[REDACTED]
PE	Physical examinations
[REDACTED]	[REDACTED]
[REDACTED]	[REDACTED]
[REDACTED]	[REDACTED]
PK	Pharmacokinetics
[REDACTED]	[REDACTED]
PO	Per os, orally
PP	Per protocol
PQC	Product Quality Complaint
[REDACTED]	[REDACTED]
PT	Prothrombin time
QD	Quaque die, once daily
[REDACTED]	[REDACTED]
QTcF	QTc calculation using Fridericia's formula
RBC	Red blood cell count
RNA	Ribonucleic acid

APPENDIX A: TABLE OF ABBREVIATIONS (CONTINUED)

Abbreviation or Specialist Term	Explanation
[REDACTED]	[REDACTED]
SAE	Serious adverse event
SARS-CoV-2	Severe acute respiratory syndrome coronavirus 2
SD	Standard deviation
SE	Standard error
SGLT	Sodium-glucose co-transporter
SGOT	Serum glutamic oxaloacetic transaminase
SGPT	Serum glutamic pyruvic transaminase
[REDACTED]	[REDACTED]
SMT	Safety Management Team
SOP	Standard operating procedure
SUSAR	Suspected unexpected serious adverse reaction
$t_{1/2}$	Terminal Half-life
TB	Tuberculosis
TBL	Total bilirubin
TEAE	Treatment emergent adverse event
TGF- β	Transforming growth factor beta
[REDACTED]	[REDACTED]
T_{max}	Time to maximum plasma concentration
TNF	Tumor necrosis factor
ULN	Upper limit of normal
[REDACTED]	[REDACTED]
VCTE	Vibration controlled transient elastography
V_z/F	Volume of distribution
WBC	White blood cell count

APPENDIX C. HEPATOTOXICITY MONITORING CRITERIA FOR INTERRUPTION AND DISCONTINUATION OF INVESTIGATIONAL PRODUCT BASED ON LIVER FUNCTION TEST ABNORMALITIES

	Laboratory Test	Action
Normal ALT and AST at baseline:	(ALT or AST > 3 x ULN but ≤ 8 x ULN) and (TBL < 2 x ULN and INR < 1.5)	Repeat ALT and AST within 48-72 hours. If elevations persist, evaluate other cause ^a of LTFs elevation. If the etiology is unknown, close monitoring required on a weekly basis until ALT or AST ≤ 3 x ULN or meet the criteria for discontinuation. Subjects (whether discontinued or not) are to be followed until the laboratory value returned to baseline.
	
 • ALT or AST > 3 x ULN and (TBL > 2 x ULN or INR > 1.5) • ALT or AST > 3 x ULN with fatigue, nausea, vomiting, right upper quadrant pain or tenderness, fever, rash, and/or eosinophilia (> 5%) • ALT or AST > 5 x ULN for more than 2 weeks • ALT or AST > 8 x ULN 	Discontinue IP and follow-up signs or symptoms until resolution.

APPENDIX C: HEPATOTOXICITY MONITORING CRITERIA FOR INTERRUPTION AND DISCONTINUATION OF INVESTIGATIONAL PRODUCT BASED ON LIVER FUNCTION TEST ABNORMALITIES (CONTINUED)

	Laboratory Test	Action
Elevated ALT and/or AST at baseline:	ALT or AST > 2 x BLM or TBL > 1.5 x BLM	Repeat ALT and AST within 48-72 hours. If elevations persist, evaluate other cause ^a of AST, ALT and TBL elevation. If the etiology is unknown, close monitoring required on a weekly basis until ALT or AST ≤ 2 x BLM and TBL ≤ 1.5 x BLM or meet the criteria for discontinuation. Subjects (whether discontinued or not) are to be followed until the laboratory value returned to baseline.
	ALT or AST > 2 x BLM and (TBL > 2 x BLM or INR increased by > 0.2 from Baseline)	Discontinue IP and follow-up signs or symptoms until resolution.
	with appearance of fatigue, nausea, vomiting, right upper quadrant pain or tenderness, fever, and rash, with or without eosinophilia (> 5%) during study	Temporarily interrupt or discontinue IP and follow-up signs or symptoms until resolution.
Elevated ALT and/or AST at baseline and BLM ^b < 2 x ULN	ALT or AST > 5 x BLM	Discontinue IP and follow-up signs or symptoms until resolution.
Elevated ALT and/or AST at baseline and BLM ≥ 2 x ULN but < 5 x ULN:	ALT or AST > 3 x BLM	Discontinue IP and follow-up signs or symptoms until resolution.

Abbreviations: ALP = alkaline phosphatase; ALT = alanine aminotransferase; AST = aspartate aminotransferase; BLM = baseline measurement(s); IP = investigational product; INR = international normalized ratio; TBL = total bilirubin; ULN = upper limit of normal.

^a Tests for causes of increases AST or ALT include infectious (Hepatitis A, Hepatitis B, Hepatitis C, Hepatitis E), acetaminophen level, toxicology screen, autoimmune (antinuclear antibodies, anti-smooth muscle antibodies, anti-liver/kidney microsomal antibodies type 1, immunoglobulin G [IgG]). Additional tests and evaluations may be requested by the medical monitor. Tests of function include serum albumin and prothrombin time (PT)/INR.

^b In subjects with screening TBL or AST or ALT, greater than 3 X ULN, baseline values should be established by at least two measurements obtained at least 4 weeks apart.

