- ^d Visit 5 Week 8 and Visit 7 Week 16 will be remote visits. Central laboratory tests, target physical examination, vital sign and weight will not be performed during these remote visits. However, if laboratory tests and/or physical examination is needed based on the Investigator's clinical judgement, an unscheduled visit should be performed at the investigational site. Urine pregnancy test kits will be provided to the subjects at Visit 4 Week 4 and Visit 6 Week 12. At Visit 5 Week 8 and Visit 7 Week 16 subjects will perform urine β -hCG test at home. IP will be dispensed at Visit 4/Week 4 and Visit 6/Week 12 for these 2 visits.
- ^e Urine pregnancy test will be performed to assess subject eligibility prior to the first administration of IP if a serum pregnancy test was not obtained within 72 hours prior to dosing (negative results required for IP administration).
- ^f Subjects who do not have a historical biopsy will undergo a liver biopsy procedure for study eligibility. The independent histopathologists will review the liver biopsy specimens to assess whether the subject meets the histological inclusion criteria. Screening liver biopsy will serve as the Baseline assessment. Subjects who discontinue after Week 20 and before Week 52 will undergo a liver biopsy procedure at ET Visit. IP should be stopped 7-10 days prior to Week 53 or ET Visit biopsy and restarted 7 days after biopsy at Week 54 if subjects participate in the active treatment phase.

^j First dose of IP should be administered at the investigative site.

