Unscheduled visits, if needed, may occur at any time, in particular for safety reasons (or efficacy reasons) as deemed necessary by the Investigator or site staff, or for any reason that the subject must return to study center as it pertains to the study (eg, to pick up additional or replacement IP). The Unscheduled Visit eCRF will be made available to the site staff, in order to record the necessary unscheduled assessments and/or procedures.

6.3. **Early Termination**

An early termination (ET) evaluation will be performed for subjects who are withdrawn from treatment for any reason as soon as possible after the decision to permanently discontinue treatment has been made.

The following evaluations will be performed as specified in the Table of Events, [Table 3](#):

- Adverse event evaluation
- Concomitant medications evaluation
- Concomitant procedures evaluation
- Counseling about pregnancy precautions and the potential risks of fetal exposure
- Complete physical examination (Section [6.5.1](#))
- Vital signs and weight (Section [6.1](#))
- 12-lead ECG (Section [6.5.2](#))
- Clinical Laboratory Evaluations (Section [6.5.3](#)):
 - Hematology panel
 - Coagulation tests
 - Chemistry panel
 - Urinalysis and urine cytology
 - Serum pregnancy test
 - Fecal occult blood test (FOBT)
- Efficacy assessment (Section [6.6](#)):
 - Liver biopsy/histology

- Investigational product (IP) return (all used and unused blister cards) and IP compliance assessment (Section 7.6)

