6.5.4. Action Plan for Monitoring Potential Hepatotoxicity

The evaluation of liver safety signals in clinical trials that enroll individuals with pre-existing liver disease presents special challenges. Refer to [Appendix C](#) for the specific guidelines for monitoring and interrupting and discontinuing subjects based upon elevations in the liver function tests after treatment with IP.

Treatment arm safety stopping rules will be finalized in consultation with members of the DMC based on the:

- Marked elevations of aminotransferases to 5 times, 10 times, or 20 times the baseline values in the active treatment and not observed or less frequent in the placebo group.
- One or more Hy’s law cases, as defined by the following preliminary parameters, based on Guidance for Industry Drug-induced Liver Injury: Premarketing Clinical Evaluation; (FDA, 2009) and modified as suggested by criteria to account for patients with pre-existing liver injury (Parks, 2013).

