11.1.1. Individual Subject Stopping Criteria

The subject will be discontinued from the study:

- If the subject has a positive FOBT at a study visit and a decrease of hemoglobin from baseline by at least 10% at that study visit or subsequent visits before next FOBT is performed
- If the subject develops a Grade 3 or higher drug-related AE by CTCAE Version 5.0 grading system
- If the subject develops a Grade 4 or higher AE by CTCAE Version 5.0 grading system
- If the subject develops decompensated liver disease such as clinically significant ascites, hepatic encephalopathy, or variceal bleeding
- If the subject meets discontinuation criteria outlined in [Appendix C](#)

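### Appendix C, normal baseline ALT and AST: a first-detected elevation with TBL exactly 2 x ULN or INR exactly 1.5 falls under neither the monitoring row nor the discontinuation row

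*Combined protocol and SAP*

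**What the plan says.** Section 6.5.4 makes Appendix C the sites' reference "for the specific guidelines for monitoring and interrupting and discontinuing subjects based upon elevations in the liver function tests after treatment with IP". Section 11.1.1 makes the appendix binding for stopping, since a subject is discontinued "If the subject meets discontinuation criteria outlined in" Appendix C.

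For subjects with normal ALT and AST at baseline, Appendix C has two rows:

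- **Monitoring row.** Condition: "ALT or AST > 3 x ULN but ≤ 8 x ULN) and (TBL < 2 x ULN and INR < 1.5". Action: repeat ALT and AST within 48-72 hours and, if the elevation persists, look for another cause. If none is found, "close monitoring required on a weekly basis until ALT or AST ≤ 3 x ULN or meet the criteria for discontinuation".
- **Discontinuation row.** Four alternatives, the first of which is "ALT or AST > 3 x ULN and (TBL > 2 x ULN or INR > 1.5". The others are ALT or AST above 3 x ULN with listed symptoms or eosinophilia, above 5 x ULN for more than 2 weeks, and above 8 x ULN.

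For subjects with elevated baseline values the monitoring trigger is "ALT or AST > 2 x BLM or TBL > 1.5 x BLM". It sets no upper limit on TBL or INR, so it has no corresponding gap.

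**The concern.** The two normal-baseline rows should together cover every subject with ALT or AST above 3 x ULN. On TBL and INR, one row stops strictly below the limit and the other starts strictly above it, so nothing is prescribed on the limit itself. Followed literally, the rule asks for less at INR 1.5 than at INR 1.4, although 1.5 is the worse value.

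The values concerned are not trivial. Screening excludes INR above 1.2 (Section 4.3, criterion 30), so 1.5 is at least 1.5 - 1.2 = 0.3 above any eligible screening value. For elevated-baseline subjects, Appendix C discontinues on an INR rise of more than 0.2 from Baseline when ALT or AST exceeds twice baseline. What is at stake is prompt repeat testing at a liver-safety threshold, not any efficacy result.

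**Working it through.** The plan gives no figure to reproduce, so the check is logical. Write A for ALT or AST and T for TBL (both in multiples of ULN), and I for INR. At first detection, without listed symptoms or eosinophilia:

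- Monitor (M): 3 < A ≤ 8 and T < 2 and I < 1.5.
- Discontinue (D): [A > 3 and (T > 2 or I > 1.5)] or A > 8. The bullet requiring more than 2 weeks above 5 x ULN cannot be met at first detection.

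**Where neither holds.** For 3 < A ≤ 8, not-D means T ≤ 2 and I ≤ 1.5. Not-M means T ≥ 2 or I ≥ 1.5. Together they leave T = 2 with I ≤ 1.5, or I = 1.5 with T ≤ 2.

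**Values put in (A = 4):**

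| T | I | Row as written |
|---|---|---|
| 1.0 | 1.4 | Monitor |
| 1.0 | 1.5 | None |
| 1.0 | 1.6 | Discontinue |
| 1.9 | 1.0 | Monitor |
| 2.0 | 1.0 | None |
| 2.1 | 1.0 | Discontinue |
| 2.1 | 1.5 | Discontinue |
| 2.0 | 1.6 | Discontinue |

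**Grid check.** Taking A = 3.1, 5, 5.1, 8 and 8.1, T = 1.9, 2.0 and 2.1, and I = 1.4, 1.5 and 1.6, there are 12 unassigned combinations. They are the four A values up to 8, each with (T, I) = (1.9, 1.5), (2.0, 1.4) and (2.0, 1.5): 4 x 3 = 12. With listed symptoms or eosinophilia the count is 0. The counts depend on the chosen grid and say nothing about how often subjects would fall there.

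**Subjects already in weekly monitoring.** That row's exit rule releases them only when ALT or AST is ≤ 3 x ULN or a discontinuation criterion is met. Reaching T = 2 or I = 1.5 is neither, so they stay in monitoring. The gap is therefore confined to first detection.

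**After the change.** With T ≤ 2 and I ≤ 1.5 in M, the grid has 0 unassigned and 0 overlapping combinations, and D is untouched. Using ≥ in the first discontinuation bullet instead also gives 0 and 0, but moves the boundary subjects into D.

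**Longest wait if the investigator does nothing.** Table 3 schedules chemistry at Weeks 0, 1, 4, 12, 20, 24, 30, 36, 42, 48, 52 and 53. Weeks 8 and 16 are remote, where "Central laboratory tests, target physical examination, vital sign and weight will not be performed during these remote visits". The intervals are 1, 3, 8, 8, 4, 6, 6, 6, 6, 4 and 1 weeks. Two of the 11 are 8 weeks: 8 x 7 = 56 days, or 50 to 62 days with ±3 days at each end. PT/INR follows the same schedule to Week 52. In the active treatment phase no chemistry interval exceeds 6 weeks.

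**The case against.** The strongest reply is that the gap is real but needs many conditions at once: normal baseline ALT and AST, first detection, a value exactly on a limit, the other marker not above its limit, no listed symptoms, and no Section 11.1.1 rule met. The exit rule in the same cell also makes the intent plain: anyone above 3 x ULN who is not discontinued is meant to be watched. A sensible investigator would not treat INR 1.5 more lightly than INR 1.4.

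The 8-week wait further assumes inaction. Section 6.2.1 provides that "Unscheduled visits, if needed, may occur at any time, in particular for safety reasons", and the footnote on remote visits directs an on-site unscheduled visit when the investigator judges laboratory tests necessary. The investigator may stop treatment (Section 3.2.1), clinically significant results are recorded as adverse events (Section 6.5.3), and the Safety Management Team and the DMC review safety data (Sections 9.9.2 and 9.9.3).

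All of this stands as to size: it makes the error minor and the long wait unlikely. It does not supply the missing instruction. Appendix C exists to prescribe action, and neither its footnotes nor Sections 6.5.4 and 11.1.1 assign the boundary values. A text-extraction fault is unlikely, because ≤ survives elsewhere in the same row. It is also fair to say that a ≥ sign in the discontinuation bullet would close the gap too. Choosing between the two is a clinical decision.

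**Conclusion.** The concern holds. In the normal-baseline part of Appendix C, a first-detected ALT or AST above 3 and up to 8 x ULN has no prescribed action when TBL is exactly 2 x ULN or INR exactly 1.5, under the conditions set out above. It is a minor wording error that should be corrected, because it sits in a stated liver-safety rule and makes the prescribed action lighter at a worse value.

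How often it could matter cannot be estimated from the documents. An INR of exactly 1.5 is plausible if INR is reported to one decimal, which is an assumption. Section 6.5.4 announces Hy's law parameters that do not appear in the public copy. They concern treatment-arm stopping, and this conclusion does not rest on them. Efficacy analyses, power and blinding are unaffected.

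**What to change.** In the normal-baseline monitoring row of Appendix C, replace the two strict signs so that the condition on TBL and INR reads TBL ≤ 2 x ULN and INR ≤ 1.5. This follows the row's own handling of the ALT/AST limit (≤ 8 for monitoring, > 8 for discontinuation) and agrees with its exit rule.

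If the sponsor's clinicians prefer to stop treatment at the limit, use ≥ for TBL and INR in the first discontinuation bullet instead, recognising that this lowers the stopping threshold. Make one change or the other, not both, since both together would put the boundary values in two rows.

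The recommended change costs two symbols in one table row and can go into the next amendment. It alters no discontinuation criterion, visit, eligibility rule or analysis.

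### Appendix C ends weekly liver monitoring when ALT or AST is at or below the limit, so a confirmed, unexplained rise in one enzyme literally ends the weekly tests as soon as they start

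*Combined protocol and SAP*

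**What the plan says.** Appendix C has two monitoring rows.

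- **Normal ALT and AST at baseline.** Entry: "ALT or AST > 3 x ULN but ≤ 8 x ULN) and (TBL < 2 x ULN and INR < 1.5". Exit: "close monitoring required on a weekly basis until ALT or AST ≤ 3 x ULN or meet the criteria for discontinuation".
- **Elevated ALT and/or AST at baseline.** Entry: "ALT or AST > 2 x BLM or TBL > 1.5 x BLM". Exit: "close monitoring required on a weekly basis until ALT or AST ≤ 2 x BLM and TBL ≤ 1.5 x BLM", or the discontinuation criteria.

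In both rows the first action is "Repeat ALT and AST within 48-72 hours". Weekly testing follows only if the elevation persists and the cause remains unknown. Both rows close with "Subjects (whether discontinued or not) are to be followed until the laboratory value returned to baseline", which sets no frequency.

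With normal baseline, the discontinuation criteria include "ALT or AST > 5 x ULN for more than 2 weeks", any value above 8 x ULN, and "ALT or AST > 3 x ULN with fatigue, nausea, vomiting, right upper quadrant pain or tenderness" (the symptom list continues). With elevated baseline they include more than 5 x BLM or more than 3 x BLM, depending on the baseline level, and more than 2 x BLM together with a TBL or INR rise.

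Section 11.1.1 makes the Appendix C discontinuation criteria individual stopping rules. Section 6.5.4 refers to Appendix C and gives no other exit rule.

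**The concern.** In the entry conditions, ALT or AST means that either enzyme is enough. If the same words carry the same meaning in the exit, one enzyme at or below the limit is enough to stop. A subject with a single raised enzyme always has the other one below the limit, so the exit is already met when weekly testing begins.

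Weekly tests are the only fixed-frequency liver tests for these subjects between scheduled panels. The normal-baseline rule on values above 5 x ULN for over 2 weeks needs serial results to be applied. Table 3, footnote d, makes Weeks 8 and 16 remote visits without central laboratory tests, so two intervals between panels last 8 weeks. The justification for Amendment 4 also relies on Appendix C monitoring when it limits the repeat ALT/AST measurement at screening to values above 3 x ULN. What is at stake is late recognition that a subject has met a stopping criterion.

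**Working it through.** **Step 1: logic of entry and exit.** The protocol states no figure to reproduce, so the check lists every combination of above the limit (H) and not above it (L), reading *or* as either or both.

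- Normal row (ALT, AST; TBL and INR within the entry limits): entry is met by HH, HL and LH. The written exit is met by HL and LH, so 2 of 3 entry states also meet the exit. With both enzymes required, 0 of 3 do.
- Elevated row (ALT, AST, TBL): 7 of the 8 states meet entry. Reading the exit as (ALT or AST) and TBL, HLL and LHL also meet it: 2 of 7. With both enzymes required, 0 of 7 do. The clause has no brackets; read as ALT, or (AST and TBL), 4 of 7 would meet it.

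These counts describe the logic and are not risks. Two illustrative cases:

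- Normal baseline, ALT 6 x ULN, AST 2.8 x ULN, normal TBL and INR: entry is met by ALT and exit by AST.
- Elevated baseline, ALT 2.5 x BLM, AST 1.5 x BLM, TBL 1.0 x BLM: entry is met by ALT, and exit by AST and TBL.

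**Step 2: scheduled chemistry panels (Table 3, footnote d applied).**

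- Year 1: Weeks 0, 1, 4, 12, 20, 24, 30, 36, 42, 48, 52 and 53. Gaps: 1, 3, 8, 8, 4, 6, 6, 6, 6, 4 and 1 weeks.
- Year 2 (active treatment phase): Weeks 55, 58, 62, 66, 70, 74, 78, 84, 90, 96 and 102. Gaps: 3, then five of 4, then four of 6 weeks.

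The 8-week gaps are only Weeks 4-12 and 12-20.

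**Step 3: worst-case delay.** Assumptions: the elevation is first seen at a scheduled panel (day 0) and confirmed on day 2 or 3; the cause is unknown; weekly draws are counted from the repeat; a site that reads the exit literally does no liver test before the next panel. G is the gap in days. Windows of ±3 days at each visit (Section 6.2) change G by up to ±6.

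- Normal row, ALT sustained at 6 x ULN: weekly draws fall on day 9-10 and day 16-17. The second is the first beyond 14 days. Delay = G − 17 to G − 16; with windows, (G − 6) − 17 to (G + 6) − 16.
- Elevated row, threshold crossed just after the repeat: the first weekly draw, day 9-10, would show it. Delay = G − 10 to G − 9; the maximum with windows is (G + 6) − 10 to (G + 6) − 9.

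| Gap | G (days) | Normal row | Normal row, windows | Elevated row | Elevated row, maximum with windows |
|---|---|---|---|---|---|
| 8 weeks | 56 | 39-40 | 33-46 | 46-47 | 52-53 |
| 6 weeks | 42 | 25-26 | 19-32 | 32-33 | 38-39 |
| 4 weeks | 28 | 11-12 | 5-18 | 18-19 | 24-25 |
| 3 weeks | 21 | 4-5 | 0-11 | 11-12 | 17-18 |

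In the normal-row example two weekly draws are usually lost before discontinuation would have been triggered. In a 3-week gap shortened to 15 days only one is lost, because the panel itself falls beyond day 14.

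**Step 4: other counting.** If weekly draws run from the first elevated draw (days 7, 14, 21), normal-row recognition is at day 21. The delays are 56 − 21 = 35, 42 − 21 = 21, 28 − 21 = 7 and 21 − 21 = 0 days. Three draws are lost, or two in a 3-week gap, where day 21 is the panel. In the elevated row the first draw is then day 7, and an 8-week gap gives 56 − 7 = 49 days (62 − 7 = 55 with windows).

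**The case against.** The strongest reply is that the wording is ambiguous and the rule still works. The cell describes a sequence: an enzyme exceeds the limit, the elevation persists, a cause is sought, and testing continues until the value falls. *Until* implies a change from the present state, and the sentence on return to baseline most naturally refers to the raised value. A rule that started and stopped on the same draw would serve no purpose, so many sites will read the exit as the raised enzyme. This stands and lowers the severity. It does not remove the defect, because no part of the protocol says so and the same table uses *or* in its entry conditions to mean either.

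The second reply is that much remains in place:

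- follow-up to baseline, whose endpoint is stricter than either exit;
- unscheduled visits (Section 6.2.1; footnote d to Table 3);
- tests requested by the medical monitor (Appendix C, footnote a);
- the symptom rows for both baselines;
- stopping for a Grade 3 or higher drug-related AE (Section 11.1.1);
- review by the SMT and the DMC (Sections 9.9.2 and 9.9.3).

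This also stands. None of these requires weekly tests. The AE rule needs a judgement that the event is drug-related, while this row concerns elevations of unknown cause; the grading cut-offs are not in the protocol, so the example cannot be tested against it.

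Third, harm needs several conditions together: one enzyme only, persistence, no cause found, a literal reading and no other test. The longest delays also need onset at Week 4 or Week 12. That is correct, and it is why the delays are given only as worst cases.

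**Conclusion.** Wrong as written: a wording error in an operative safety rule, of low severity. The logical defect is certain under the literal reading: 2 of 3 entry states in the normal row and 2 of 7 in the elevated row meet the exit at once.

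The delays in the table rest on the Step 3 assumptions, chiefly that no liver test is done before the next panel and that weekly draws run from the repeat. The protocol gives no rate of isolated, unexplained elevations and no information on how sites read the rule, so the number of subjects affected cannot be estimated.

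Three stronger readings are not supported:

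- A reader might infer that liver follow-up ceases. It does not: only the weekly frequency ends.
- A reader might infer that the stopping criteria are disabled. They are not: any later result that meets them still stops treatment, and what suffers is timely recognition.
- A reader might infer that the sponsor meant to release one-enzyme elevations from monitoring. The sequence in the cell points the other way.

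**What to change.** Change only the enzyme term of each exit.

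- Normal baseline: weekly until *ALT and AST are both ≤ 3 x ULN*, or the discontinuation criteria are met.
- Elevated baseline: weekly until *ALT and AST are both ≤ 2 x BLM and TBL ≤ 1.5 x BLM*, or the discontinuation criteria are met.

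Keep all limits and the rest of each row. This also removes the bracketing ambiguity in the elevated row. Do not define the exit as the full negation of the entry condition: in the normal row, TBL of 2 x ULN or more, or INR of 1.5 or more, would then count as an exit.

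The cost is a few words in two table cells, at the next amendment or in a clarification letter to sites. Sites that already follow the raised enzyme do nothing new. At a site that had read the row literally, the normal-baseline example adds two draws, or three if counted from the first elevated draw, and fewer in a short 3-week gap.
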